### ***Secondary objectives***

To assess whether the effects of transdermal GTN, started within 3 hours of symptom onset in the prehospital setting, on functional outcome at 90 days are consistent across specific subgroups of patients, i.e., those with 1. ischaemic stroke; 2. ischaemic stroke treated with endovascular techniques; or 3. intracerebral haemorrhage.

To assess the effect of GTN on collaterals, size of the ischemic core and salvageable brain tissue on admission to the hospital.

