### 4.2 Inclusion criteria

In order to be eligible to participate in this study, a subject must meet all of the following criteria:

1. Age 18 years or older;
2. Probable diagnosis of acute stroke, as assessed by the paramedic in the prehospital setting;
3. Score of 2 or 3 on the Face Arm Speech Test (FAST, Appendix 3);
4. Systolic blood pressure  $\geq$  140 mm Hg;
5. Possibility to start the trial treatment within 3 hours of symptom onset;
6. Intention to transport the patient to one of the participating hospitals;
7. Written informed consent (deferred).

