### 8.1.3 Other study parameters

Baseline characteristics, assessed as part of routine clinical care at the time of the initial assessment by the paramedics. The last assessments before study inclusion should be reported.

- Age; sex;
- Vital signs: systolic and diastolic blood pressure, and pulse;
- Score on the Glasgow Coma Scale;
- Score on the FAST;
- Time of stroke onset according to paramedics;
- Date and time of randomisation.

Baseline characteristics, assessed as part of usual clinical care at the time of hospital admission:

- Comorbidities/medical history: atrial fibrillation; diabetes mellitus; hypertension; pre-stroke mRS;
- Concurrent drugs: use of any blood-pressure-lowering drug in the 3 days before randomisation;
- Dates and times according to treating physician: stroke onset, hospital admission;
- Vital signs: blood pressure; pulse; body temperature;
- Neurological examination: NIHSS (see paragraph 8.3.4 and Appendix 4); (expected) location of the lesion (left or right hemisphere; posterior fossa);
- Laboratory examinations (see paragraph 8.3.6);
- Imaging results: stroke type: ischaemic stroke, intracerebral haemorrhage, or other relevant finding (see paragraph 8.3.7);
- Treatment restrictions (see paragraph 8.3.9);
- Stroke treatment: IVT with alteplase; IAT.

First 7 days or until discharge, if earlier:

- Vital signs: blood pressure and pulse at hourly intervals in the first 6 hours, at 2-hourly intervals between 6 and 24 hours, and daily thereafter;

- Final diagnosis (ischaemic stroke; intracerebral haemorrhage; other diagnosis);
- Cause of ischaemic stroke according to TOAST criteria;
- Treatment restrictions.
- Stroke treatment: early blood pressure reduction as acute treatment of intracerebral haemorrhage; surgery for intracerebral haemorrhage or decompressive hemicraniectomy for ischaemic stroke.

Safety parameters in first 7 days or until discharge, if earlier:

- Any serious adverse event (see paragraph 9.2.2);
- Hypotension requiring clinical intervention;
- Hypertension requiring clinical intervention;
- ‘Symptomatic intracerebral haemorrhage (sICH) scored according to the Heidelberg Bleeding Classification, with the addition of sICH that led to death and that was identified as the predominant cause of the neurologic deterioration.

Prehospital data that will be recorded:

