### 10.2 Primary outcome

The primary effect estimate will be a shift in the mRS score at 90 days ( $\pm$  14 days) assessed by means of ordinal logistic regression, and will be expressed as a common odds ratio with 95% confidence interval. The assumption of proportional odds will be assessed using the likelihood ratio test. The statistical analyses will be performed according to the intention-to-treat principle and adjusted for relevant baseline characteristics including age, sex, stroke type, score on the FAST at study inclusion, time of symptom onset to randomisation, pre-stroke score on the mRS, and ambulance region.

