#### 10.4 Subgroup analyses

Comparison of the primary outcome in the intervention group vs. control will be performed in the following pre-specified subgroups:

- Age ( $\leq 70$ ,  $> 70$  years);
- Sex (male, female);
- Stroke type (ischaemic stroke, intracerebral haemorrhage);
- In patients with ischaemic stroke: visible occlusion of the proximal intracranial arteries (internal carotid artery (ICA); basilar artery (BA); first or second segment middle cerebral artery (MCA), anterior cerebral artery (ACA), or posterior cerebral artery (PCA));
- Intravenous thrombolysis (yes; no);
- Intra-arterial treatment (yes; no);
- Blood pressure, dichotomised at the median;
- Stroke severity at presentation in the hospital;
- Time to treatment ( $< 90$  minutes;  $\geq 90$  minutes).

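### Section 10.4 examines age, blood pressure and time to treatment only as two-group splits; if the GTN effect changes steadily with age or blood pressure, a split keeps only about 64% of the information on that trend

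*Protocol*

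**What the plan says.** Section 10.4 (Subgroup analyses) describes the method in one sentence: "Comparison of the primary outcome in the intervention group vs. control will be performed in the following pre-specified subgroups". Three of the listed items are cuts of a quantitative variable: age at 70 years, "Blood pressure, dichotomised at the median", and time to treatment at 90 minutes. The section does not say whether systolic or diastolic pressure is meant, or which measurement. It mentions no treatment-by-covariate term. The one plan in the protocol to test for interaction, in Appendix 2, concerns the treatments of the different CONTRAST trials.

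Section 8.1.3 has the paramedics record, before inclusion, age and "Vital signs: systolic and diastolic blood pressure, and pulse", together with onset time and the date and time of randomisation. It lists blood pressure again among the characteristics taken at hospital admission.

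Section 10.2 gives the primary effect as a shift on the mRS "assessed by means of ordinal logistic regression, and will be expressed as a common odds ratio with 95% confidence interval". Age and onset-to-randomisation time are among its named adjustment covariates; blood pressure is not.

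**The concern.** A two-group split treats all patients on one side of the cut as alike and places near neighbours on either side of it in different groups. With a floor of "Systolic blood pressure $\geq$ 140 mm Hg", a patient at 141 mm Hg is pooled with one just under the median, and two patients a few mm Hg apart across the median are contrasted. If the effect changes gradually, this weakens the comparison. The trial is sized for the main effect (Section 4.4), so power to see variation in effect is limited from the start. The risk is that a real gradient goes unseen and is reported as consistency.

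The variables matter to this trial's own rationale. Blood pressure reduction is one of the two proposed mechanisms. On time, Section 1.8 reports more apparent benefit with shorter delay in the pooled earlier trials, but a tendency towards harm in RIGHT-2 patients treated within one hour. A single cut at 90 minutes is a blunt tool for describing that relation.

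**Working it through.** The protocol gives no figure for information or power in the subgroup analyses, so there is none to reproduce.

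**Inputs.** From the protocol: the cuts in Section 10.4, the 140 mm Hg floor and the lower age limit of 18 in Section 4.2, the ordinal model in Section 10.2, and 1400 patients in Section 4.4. Assumed: the means, SDs and shapes of age and systolic pressure.

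**1. Information kept on a linear trend.** When X is replaced by the indicator X > c, the share kept is the squared correlation of X with that indicator. For a normal X with a proportion p below the cut and z the matching normal quantile, this is φ(z)² / [p(1 − p)]. At the median it is 2/π = 0.637, a loss of 36.3%.

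| Covariate and cut | Assumption | Loss |
|---|---|---|
| Normal, median cut | – | 36.3% |
| Age, cut at 70 | normal, mean 65–76, SD 11–15 | 36–43% |
| Age, cut at 70 | limited to 18–100, mean 70–74, SD 13 | 35–36% |
| Systolic pressure, median cut | normal with mean 150–180, SD 25–28, truncated at 140 | 34–37% |
| Uniform, median cut | shape extreme | 25% |
| Exponential, median cut | shape extreme | 52% |

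A loss of 35% to 36.3% is equivalent to using about 910 to 890 of 1400 patients for this question (1400 × 0.65 = 910; 1400 × 0.637 = 892).

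**2. Power.** Take an interaction with 80% power at two-sided 5% when X is continuous, so the expected z is 1.96 + 0.84 = 2.80. After a split, power is 1 − Φ(1.96 − 2.80 × √share kept):

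- share 0.637: 61%
- share 0.65: 62%
- share 0.75 (uniform): 68%
- share 0.48 (exponential): 49%

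**3. Check in the planned type of model.** A proportional-odds simulation used N = 1400, a seven-level mRS, a normal covariate, an interaction of 0.27 log-odds per SD and 120 runs. The mean interaction z was 2.79 continuous and 2.23 after a median split. The information ratio is (2.23/2.79)² = 0.64, and power was 80% against 59%. With 120 runs, each power figure has a standard error of about 4 percentage points.

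**4. When the effect is a step, not a gradient.** For a normal covariate and a step at percentile p ≥ 50%, the median split keeps (1 − p)/p and a linear term keeps φ(z)² / [p(1 − p)].

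- Step at the median: split 1.00, linear 0.64.
- Step at the 75th percentile: split 0.25/0.75 = 0.33, linear 0.318²/0.1875 = 0.54.
- The two are equal where 1 − p = φ(z), at about the 62nd percentile and, by symmetry, the 38th.

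The split is therefore the better test only when the true step lies roughly between the 38th and 62nd percentiles.

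No loss is computed for time to treatment. Its distribution is not given, and 90 minutes need not be near its median.

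**The case against.** **The SAP could add a continuous test.** Section 10.1 leaves the technical description and the subgroup analyses to the SAP, and a continuous interaction alongside these groups would contradict nothing. That is true, but Section 10.4 already fixes the cuts and describes the analysis as a comparison within them. The point concerns what the protocol states, and it lapses if the SAP has the continuous test.

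**The cuts are prespecified rules.** They leave no room to choose a cut after seeing outcomes, and a median gives balanced groups. This stands as a defence against data-driven selection. It does not recover the lost information.

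**The size is conditional.** This stands in full. The 36% and the fall from 80% to about 60% hold for a linear gradient and a near-normal covariate. A reader might apply them to a pattern such as benefit only at high pressure. That is a threshold, and step 4 of the working shows that either test can then be the better one.

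**The 80% benchmark is hypothetical.** A reader might infer that the trial has 80% power for some interaction. Section 4.4 powers only the main effect. The figure compares two analyses of the same effect.

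**Section 2.** A reader might infer that the secondary objective, whether effects "are consistent across specific subgroups of patients", is compromised. It is not: the groups named there are ischaemic stroke, ischaemic stroke treated endovascularly, and intracerebral haemorrhage. None is a cut of a continuous variable.

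**Conclusion.** The point holds as a cheap improvement to the subgroup analyses. Under a steady change in effect with age or blood pressure, the split discards about 36% of the information on that change, and 25% to 52% across extreme shapes. Power that would be 80% on the continuous scale falls to about 60%. This rests on assumed covariate distributions and on linearity on the log-odds scale. If the effect steps at the cut, the split loses nothing. For time to treatment the same reasoning applies without a figure. The primary estimate, its power and the Section 2 consistency objective are unaffected.

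**What to change.** In Section 10.4, state that effect modification by age, blood pressure and time is tested as treatment by continuous age, treatment by continuous prehospital (pre-randomisation) systolic blood pressure, and treatment by continuous onset-to-randomisation time, each in the adjusted ordinal model of Section 10.2. Add a spline version of each as a check on linearity. Blood pressure needs a main-effect term in its model, since Section 10.2 does not name it as a covariate. Keep the two-group results for display only.

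Naming prehospital systolic pressure also settles which measurement is used. Admission pressure is taken after treatment may have started, and Section 8.1.2 lists it as a secondary outcome. Section 1.8 reports that GTN had lowered systolic pressure by 5.8 mm Hg by admission in RIGHT-2.

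The cost is a few lines of protocol or SAP text and of code, with no new data, and it should be done before unblinding. The downside is that the main test assumes a linear gradient on the log-odds scale and is less efficient than the split if the true effect is a step near the cut.

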### 3. STUDY DESIGN

This is a multicentre, prospective randomised, open clinical trial with blinded outcome assessment (PROBE) of transdermal GTN in a dose of 5 mg/day for one day, in 1400 adult patients with suspected stroke. Patients will be recruited in a maximum of 10 ambulance regions in the Netherlands. Patients will be included in the study by a paramedic before hospital admission. Study treatment will be started in the prehospital phase, and continued in the admitting hospital. MR ASAP is part of a consortium of 5 acute stroke trials conducted by the Dutch 'Collaboration for New Treatments of Acute Stroke' (CONTRAST, see Appendix 1). The trial will be performed according to ICH-GCP principles, the Declaration of Helsinki as most recently amended in 2013, and national regulatory requirements. Because the majority of patients will be incapacitated and because the informed consent procedure should not delay the process of transporting the patient to the hospital, we will use a deferred consent procedure.

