##### At 24 hours ( $\pm 4$ hours):

- Treatment with intravenous thrombolysis;
- Intra-arterial treatment;
- Vital signs: systolic and diastolic blood pressure, pulse, and body temperature;
- Neurological deficit, as assessed with the NIHSS;

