**Considerations**

(1) The CONTRAST studies are independent RCT's. Patients who have been included in MR ASAP may also be included in one of the intervention trials for ischemic or for haemorrhagic stroke. Being eligible for two trials at the same time raises questions whether the trials influence each other's results. Therefore, we will perform pre-specified subgroup analyses to test for interaction between the different performed treatments. Further, part of the potential treatment effect in MR ASAP will be represented in the baseline characteristics measured at inclusion in the second trial, such as collaterals, blood pressure and NIHSS, which we will adjust for in all analyses.

(2) At the first ER (either a primary stroke centre or a participating intervention centre), all patients with a probable diagnosis of acute stroke will undergo non-contrast CT to differentiate between acute cerebral infarction or acute intracranial haemorrhage. When the first ER is a primary stroke centre and the patient could be eligible for the DUTCH ICH TRIAL, MR CLEAN-MED or MR CLEAN-LATE study, the patient should be transferred to a participating intervention centre (where inclusion in one of these studies, randomization and treatment takes place).

(3) Patients arriving at a primary stroke centre first, will never be eligible for the MR CLEAN-NO IV, since intravenous thrombolysis with alteplase (IVT) cannot be withheld until after patient transfer to the participating intervention centre. Patients who are eligible for inclusion in MR CLEAN-NO IV (primary presentation at intervention centre, <4.5 hours + eligible for IVT) will not be included in MR CLEAN-MED. Patients presenting at the primary stroke center within 6 hours (both eligible or not eligible for IVT), could be eligible for the MR CLEAN-MED. Importantly by this scheme, competition between the intervention trials will not occur.

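### Section 10.4 defines effect subgroups by hospital severity, thrombolysis and intra-arterial treatment, which normally arise after GTN has started, so these contrasts can be biased and should be redefined or labelled

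*Protocol*

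**What the plan says.** On timing, Section 3 states: "Study treatment will be started in the prehospital phase, and continued in the admitting hospital".

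Section 10.4 then lists, among the prespecified subgroups for the primary outcome, "Stroke severity at presentation in the hospital", "Intravenous thrombolysis (yes; no)" and "Intra-arterial treatment (yes; no)". It also lists "Blood pressure, dichotomised at the median", with no time point, and "Time to treatment", cut at 90 minutes.

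Elsewhere the same variables have another role:

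- Section 8.1.2 gives "Treatment with intravenous thrombolysis" and intra-arterial treatment as secondary outcomes at 24 hours, and blood pressure and collaterals as secondary outcomes on admission.
- Section 8.3.4 schedules the NIHSS at admission and at 24 hours only. Section 8.1.3 files the admission value as a hospital baseline characteristic.
- Appendix 2, consideration (1), expects part of the MR ASAP effect to show in the characteristics recorded on entry to a second trial, "such as collaterals, blood pressure and NIHSS, which we will adjust for in all analyses".
- Section 2 makes consistency of effect in endovascularly treated patients a secondary objective.
- Section 8.2 leaves treating physicians aware of the allocation.

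The covariates named in Section 10.2 include prehospital FAST, onset-to-randomisation time and pre-stroke mRS, but not collaterals, blood pressure or NIHSS.

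**The concern.** A subgroup comparison keeps the protection of randomisation only if the arms fall into the subgroups by the same process. Here the patch is normally on before the grouping variable is determined. If GTN makes some patients milder by arrival, the mild stratum in the GTN arm contains patients who would have been in the severe stratum as controls, and the two arms within a stratum are no longer alike. For thrombolysis and intra-arterial treatment a second route is open: the decisions are taken by people who know the allocation, so membership could differ by arm without any drug effect.

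Such a shift is not far-fetched in this protocol. Section 1.10 relies on blood pressure falling within 15 minutes and on better collaterals before recanalisation. Section 1.8 reports a 5.8 mm Hg lower systolic pressure at admission with GTN in RIGHT-2.

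These subgroups will also be read closely. Severe stroke was one of the groups with a tendency towards harm in RIGHT-2, and higher endovascular treatment rates are part of the argument for expecting a different result here.

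**Working it through.** No figure in the protocol states the size of this problem, so the check is an illustration built on the design effect.

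**Design effect.** Section 4.4 assumes 48% versus 41% with mRS 3 to 6. The implied common odds ratio is (0.41/0.59)/(0.48/0.52) = 0.753.

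**Simulation (structure and coefficients assumed).** Each scenario has 60,000 patients, half per arm. With S a pre-randomisation severity measure, U an unmeasured prognostic factor, and T = 1 for GTN:

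- Admission severity M = 0.6·S + r·U − d·T + noise, with SD about 1 and r = 0 or 0.5.
- Latent outcome = 1.2·M + 0.5·U + b·T + logistic noise. It is cut into seven categories so that controls have proportions 0.10, 0.20, 0.22, 0.15, 0.12, 0.08 and 0.13 for mRS 0 to 6. The last four sum to 0.48, as in Section 4.4.

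Proportional odds models adjusted for S were fitted overall, in halves split at the median of M, and in halves split at the median of S. The last column adds M as a covariate.

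| Shift d, direct effect b | r | Overall OR | Halves by admission severity | Halves by pre-randomisation severity | Adjusted for M |
|---|---|---|---|---|---|
| 0, 0 | 0 | 1.00 | 0.99, 0.99 | 1.02, 0.98 | 1.00 |
| 0, 0 | 0.5 | 1.00 | 0.98, 1.02 | 1.00, 1.01 | 1.01 |
| 0, −0.28 | 0 | 0.78 | 0.76, 0.78 | 0.78, 0.78 | 0.76 |
| 0, −0.28 | 0.5 | 0.80 | 0.79, 0.78 | 0.80, 0.80 | 0.76 |
| 0.15, −0.14 | 0 | 0.76 | 0.80, 0.81 | 0.77, 0.76 | 0.86 |
| 0.15, −0.14 | 0.5 | 0.80 | 0.85, 0.88 | 0.77, 0.82 | 0.94 |
| 0.3, 0 | 0 | 0.75 | 0.88, 0.88 | 0.75, 0.75 | 1.02 |
| 0.3, 0 | 0.5 | 0.75 | 0.91, 0.89 | 0.74, 0.75 | 1.10 |

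The simulation error of a log odds ratio in one half is about √(12/(30,000 × 0.973)) = 0.02, where 0.973 is 1 minus the sum of the cubed control proportions. Differences of two or three hundredths between halves are therefore noise.

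With no shift (d = 0), splitting on admission severity does no harm. With full mediation (d = 0.3, b = 0), neither half recovers the overall effect, and about 56% of GTN patients but 44% of controls fall in the milder half. The pre-randomisation split recovers the overall effect to within simulation error in every scenario.

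**Blood pressure, only if the admission value were meant.** With a 5.8 mm Hg difference and a split at the pooled median, the share of GTN patients in the lower half is Φ(2.9/SD). For assumed SDs of 20, 25 and 30 mm Hg this is 55.8%, 54.6% and 53.9%, against 44.2%, 45.4% and 46.1% of controls. The paramedic value recorded before inclusion (Section 8.1.3) has no such problem.

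**Time.** Under Section 5.1 controls receive standard care alone, so they have no start of trial treatment to time. Onset-to-randomisation time, already a covariate in Section 10.2, exists in both arms.

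**The case against.** The strongest reply is that bias needs a shift, and no shift has been shown: if GTN and knowledge of allocation leave these variables alone, the subgroups are valid. That is correct, and it is why the point says the contrasts can be biased, not that they are. Section 5.1 also allows enrolment during transfer between hospitals; for those patients the first hospital assessment may precede GTN.

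It can also be said that Section 10.1 leaves subgroup analyses to the SAP. That disposes of some detail: 10.4 neither prescribes separate significance tests nor excludes interaction terms, so nothing is raised on that. It does not dispose of the subgroup definitions, because 10.4 already fixes them. For blood pressure and time, the reply that these are wording clarifications stands.

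A reader might infer from Appendix 2 that the MR ASAP effect itself will be adjusted for collaterals, blood pressure and NIHSS. The documents do not support this. The sentence concerns values on entry to the second trial, where they are true baseline values and adjustment is sound, and Section 10.2 names none of the three. What remains is an ambiguity of scope: the wording covers all analyses, the list in 10.2 is not closed, and Section 8.1.3 calls admission pressure and NIHSS baseline characteristics.

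A reader might also extend the point to visible arterial occlusion. The protocol neither lists occlusion as an outcome nor names it as carrying the effect, so the argument does not reach it.

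**Conclusion.** The point holds for three subgroups: severity at hospital presentation, thrombolysis and intra-arterial treatment. Thrombolysis and intra-arterial treatment are at once secondary outcomes and effect strata, and NIHSS is named by the protocol as a carrier of the effect. The endovascular secondary objective rests on one of these strata.

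The size depends on how far treatment moves the grouping variable. It ranges from nothing, with no shift, to an overall odds ratio of about 0.75 appearing as about 0.88 to 0.91 in both severity halves, under a 0.3 SD shift with full mediation. With half the shift and a direct effect as well, 0.76 to 0.80 overall appears as 0.80 to 0.88. The shifts, coefficients and blood pressure SDs are assumptions; only the 48% versus 41% and the 5.8 mm Hg come from the protocol.

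This should be fixed, but it concerns secondary analyses. The primary model as listed in Section 10.2 does not contain these variables.

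**What to change.** In Section 10.4:

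- Define the severity subgroup from prehospital data already collected: FAST 2 versus 3, and the Glasgow Coma Scale.
- State that the blood pressure subgroup uses the paramedic's last value before inclusion.
- Replace "Time to treatment" with onset-to-randomisation time, as in Section 10.2.
- Keep the thrombolysis, intra-arterial treatment and hospital-severity subgroups, including the endovascular secondary objective, but label them post-randomisation and exploratory.

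In Appendix 2, state that adjustment for collaterals, blood pressure and NIHSS applies to the second trial's analyses and not to MR ASAP's effect estimates.

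No new data are needed. There are two costs. FAST is a coarser severity measure than the NIHSS, since eligibility admits only scores of 2 and 3. The endovascular comparison, which matters to the trial's rationale, carries an exploratory label.
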